- 1) **Date:** 12/18/23
- 2) **Study Title:** Supplementation with a Next Generation Synbiotic in Individuals with Overweight or Obesity: A Triple-Blinded Randomized Controlled Trial
- 3) **Principal Investigator (must be a TCU faculty or staff):** [name]
- 4) **College/School:** Texas Christian University
- 5) **Other Investigators:** List all faculty, staff, and students conducting the study. For those not affiliated with TCU, please provide their names and institution.
[name], [name], [name], [name], [name], [name], [name], [name], [name], [name], and [name]
- 6) **If you have internal or external funding for this project –**
Funding Agency: The supplement company Pendulum will provide the product (probiotic and placebo with a market value of \$50,400). The Dean's Opportunity Fund will provide \$49,512 for blood analyses, blood and stool sample tubes, and stool sample whole genome sequencing. [name] will provide part of her start up funds (\$6,000) for participants compensation. **Project #: IRB#2023-345** **Date for Funding:** November 2023
- 7) **If you intend to seek/are seeking internal/external funding for this project –**
Funding Agency: TCU Graduate SERC Grant
Amount Requested From Funding Agency: \$2,000
Due Date for Funding Proposal: October 23rd, 2023
- 8) **Purpose: Describe the objectives and hypotheses of the study and what you expect to learn or demonstrate:** Our proposed triple-blinded, placebo controlled, randomized clinical trial is divided into two stages.
The first stage will consist of exploring the effect of next generation synbiotic supplementation for 12 weeks on body composition, insulin sensitivity, gut microbiota composition and diversity, depression, anxiety, and food cravings in 60 individuals with overweight or obesity who have no diagnosis of diabetes mellitus (DM). For this first stage, we hypothesize that this next generation synbiotic will decrease adiposity, overall body weight, anxiety, depression, and food cravings and increase insulin sensitivity, and gut microbiota diversity. We also hypothesize that the levels of bacterial species in the symbiotic will increase in the gut microbiome.
The second stage will only be conducted if enough external funds are ensured by using the results from the first stage as preliminary data. The second stage would consist of performing 16S rRNA on blood samples to analyze microbial composition in blood, and metabolomic analysis to evaluate the effect of the probiotic on gut-derived metabolites in blood and stools. The hypothesis of this second stage of the project is that the next generation symbiotic will change blood microbial composition as well as the presence and concentration of gut-derived metabolites in blood and stool samples. If relationships exists between changes in body composition, insulin sensitivity, depression, anxiety, or cravings (first stage variables) with blood microbial composition and derived-

metabolites (second stage variables), we could show not only a cause-effect relationship but also the mechanism of action through which the next generation symbiotic acts.

9) Background: Describe the theory or data supporting the objectives of the study and include a bibliography of key references as applicable.

Obesity is a strong risk factor for the development of the majority of the leading causes of death.¹ Recent research has pointed to the gut microbiota as a potential mechanism of action through which body weight can be regulated.² The gut microbiota of people with obesity has a lower alpha diversity³ and lower abundance of *Akkermansia muciniphila*.⁴⁻⁷

Next Generation Probiotics have been created as a result of recent scientific advances.⁸ *A. muciniphila* is one of the next generation species that has independently shown anti-obesity potential.⁹ *A. muciniphila* is inversely correlated with body weight, fat mass, fasting glucose, and hedonic eating.¹⁰⁻¹² *A. muciniphila* is a gram-negative anaerobic bacteria and therefore it is difficult to grow in the lab. Pendulum® (the company that will donate the product to TCU), which possesses a patented strain of *A. muciniphila*, has been able to create an oxygen-free manufacturing process to cultivate and grow this bacterial specie. In mice, its administration has shown to be sufficient to protect from diet induced obesity and insulin resistance.¹³ In humans, *A. muciniphila* supplementation at a concentration of 10^{10} bacteria per day for 12 weeks is safe and effective and can improve metabolic parameters such as body weight, fat mass, and insulin resistance in volunteers with overweight or obesity who are insulin-resistant.¹⁴ In addition to physical benefits, preliminary research indicates *A. muciniphila* to have potential psychological benefits.¹⁵ In mice and humans, depression and anxiety are significantly associated with decreased *A. muciniphila* abundance.¹⁶⁻²² Furthermore, *A. muciniphila* supplementation in mice with chronic restraint stress-induced depression resulted in significantly diminished depression-like behavior.¹⁹ Additionally, FMT from healthy patients decreased anxiety and depression in patients with refractory irritable bowel syndrome or ulcerative colitis, changes that were associated with higher abundance of *A. muciniphila*.^{21,22}

Synbiotics combine probiotics (alive bacteria) and prebiotics (bacteria food) in order to improve microorganism survival and activity within the host.²³ The synbiotic that will be used in this trial contains the oligosaccharide-degrading probiotics, *A. muciniphila* and *Bifidobacterium infantis*; butyrate producers such as *Clostridium beijerinckii*, *Anaerobutyricum hallii*, and *Clostridium butyricum*; and chicory-derived inulin, a prebiotic dietary fiber. Butyrate is a gut-derived short chain fatty acid suspected to play a role in weight regulation and insulin resistance.²⁴ Butyrate administration in mice models of obesity improves weight and fat mass regulation, increases lipid oxidation in brown adipose and liver tissue, and stimulates the production of gut-derived neuropeptides involved in energy homeostasis and food intake, such as GIP, GLP-1, PYY, and serotonin, and decreases fasting insulin.²⁵⁻²⁷ A previous pilot clinical trial indicated the synbiotic that will be used in the current study to be safe and tolerable as well as effective in reducing HbA1c and improving post-prandial glucose control in individuals with type 2 diabetes mellitus (T2DM) and overweight or obesity,²⁸ however, no studies have analyzed the effect of the synbiotic on body composition, anxiety, and depression in individuals with overweight who do not have T2DM.

References:

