In the first visit, participants will come for 45 minutes to the Rickel Department where they will receive a complete explanation of the protocol and will process to sign the "Informed Consent to Participate in Research and Authorization to Collect, Use, and Share their Health Information" if agreeing to participate. Participants' height and weight will be measured to ensure they meet BMI inclusion criteria. Height will be measured using a standard stadiometer and weight will be measured using a standard calibrated digital scale. Their race will be asked to help in data interpretation. Height, weight, race and other information relevant to antibiotic prescription such as date of birth, allergies to medications, and preferred pharmacy will be collected at this time point using our document titled "checklist 2". All symbiotic and placebo bottles will be entirely similar with exemption of individual codes that will vary every 3 bottles. This is because each participant will be provided at the beginning of the study with 3 bottles (with similar code) to ensure enough supply for the 12-week supplement intervention. The company Pendulum will perform an *a priori* randomization of the entire study by using blocked randomization with randomly selected blocked sizes with the intention to reduce bias and ensure balance between groups. This randomization will be added into an Excel document in which they will specify the order of the participant in column 1 (example: Participant 001, Participant 002), the code of the bottles in column 2, and the interpretation of the code (placebo vs probiotic) in column 3. A researcher, independent from this study ([name]), will save in different protected locations (Box, secured laptop, protected USB) the randomization document. [name] will share with [name] an Excel document containing column 1 and column 2 of the provided document (the order of participant and the code of the bottles, without the interpretation of each code). [name] will use the supplement code as the participants' IDs and study data will be added to this Excel document. Both documents, from, [name] and from [name], will be merged at the end of the study, once data has been analyzed to figure out the intervention group to which each participant belonged. During the first

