If participants withdraw from their study the data collected up to that point will remain available for research purposes with the intention to use intent to treat analysis. Blood and stool samples will be stored in [name] lab located within the Rickel building room 259. For the first stage of the project, blood samples will be analyzed at [name] lab room 259. Once the Nutritional Sciences Department laboratory has been finalized, samples will be transferred to the Nutritional Sciences Department and further storage and analyses could take place here (BASS, room 1203). If enough funds become available to perform the second stage of the study, blood and stool samples (which will be identified by fabricated ID) will be sent to Baylor College of Medicine and to Metabolon for posterior 16S rRNA/WMS and mass spectrometry analyses, respectively. For statistical analysis of the first stage, two sample T-tests will be used to compare within (pre- versus post- values on each group) and between-group (placebo versus probiotic) differences in body composition, adherence, metabolic, dietary, and psychological variables. SPSS will be used for statistical analysis. A p value <0.05 will be considered as statistically significant. Dietetic variables collected via the NCI Automated Self-Administered 24-hour Dietary Assessment Tool including protein, carbohydrate, fat, and fiber will be controlled statistically in the case that significant intra-individual or between-group differences are observed.

20) Check List for the Items That Need to be Submitted: Please submit protocol and consent documents separately in MS word, supplemental documents (interview guides, surveys, recruitment materials etc. can be submitted as separate pdfs) before submitting the materials electronically to the IRB. To prevent any delay in the approval of your protocol, use the most recent template for the protocol, consent document, and HIPAA form by downloading them from <https://research.tcu.edu/research-compliance/irb/irb-forms-templates/> each time you prepare your materials.

a. Protocol	X
b. Consent document	X
c. Protecting Human Research Participants Training complete for each investigator	X
d. Recruitment flyers, letters, ads, etc.	X
e. Questionnaires or other documents utilized in screening and data collection	X

Principal Investigator Assurance

21) By signing below, I certify to the following:

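### Section 8 says that related changes in stage 1 outcomes and stage 2 markers could show cause-effect and mechanism; such relationships can support only an exploratory association

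*Combined protocol and SAP*

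**What the plan says.** Section 8 (Purpose) gives the stage 1 expectation that the product moves the outcomes: "we hypothesize that this next generation synbiotic will decrease adiposity, overall body weight, anxiety, depression, and food cravings and increase insulin sensitivity". It then gives the stage 2 expectation that the product also moves the markers: "The hypothesis of this second stage of the project is that the next generation symbiotic will change blood microbial composition", together with gut-derived metabolites in blood and stool. The next sentence links the two. Its condition is "If relationships exists between changes in body composition, insulin sensitivity, depression, anxiety, or cravings (first stage variables) with blood microbial composition" and metabolites. Its conclusion is "we could show not only a cause-effect relationship but also the mechanism of action through which the next generation symbiotic acts".

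No section names an analysis for this link:

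- Section 19 (Data Analyses) plans t-tests for stage 1, with the threshold "A p value <0.05 will be considered as statistically significant". It provides for statistical control of dietary variables only if significant differences in them are seen.
- Section 14 (Study Procedures, Stage 2) plans a comparison of blood microbiome composition before and after the intervention, plus alpha and beta diversity. It refers the metabolomic data analyses to a cited article.

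Section 8 makes stage 2 conditional on external funding.

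**The concern.** The sentence treats an association between two post-randomisation changes as evidence of mechanism. The markers are not randomised; only the product is. If the hypotheses in section 8 are both true, arm is a common cause of the outcome change and the marker change. The two can then be correlated across the whole sample although neither affects the other, so the evidence the plan would accept for a mechanism is expected even where there is none.

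Timing does not help. Outcomes and stage 2 blood markers are taken at the second and third visits, and the last stool sample is collected around the end of supplementation. The additional blood collection at the first visit precedes supplementation. Nothing is measured in between that would show a marker moving before an outcome.

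At stake is what stage 2 may claim. A reported mechanism could go beyond what the design can show.

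**Working it through.** The plan has no correlation, power or sample-size figure to reproduce, so the check asks what the stated condition would yield with no mechanism at all.

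**Inputs from the documents.** 60 participants (sections 8 and 11); significance at p < 0.05 (section 19); randomisation described in section 14 as "blocked randomization with randomly selected blocked sizes with the intention to reduce bias and ensure balance between groups".

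**Assumptions.** The allocation ratio is not stated; 1:1 (30 per arm) is assumed. Testing is taken as two-sided. No effect sizes are given, so a range of 0.2 to 1.5 SD of the change is used.

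**No-mechanism model.** Marker change = d1 × arm + e1; outcome change = d2 × arm + e2. The errors are independent with SD 1, and there is no path from marker to outcome. At 1:1 the arm indicator has variance 1/4, so the correlation pooled over arms is

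r = (d1·d2/4) / √[(1 + d1²/4)(1 + d2²/4)],

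which for d1 = d2 = d reduces to (d²/4)/(1 + d²/4). Examples: d = 0.74 gives 0.1369/1.1369 = 0.120; d = 1.0 gives 0.25/1.25 = 0.200; d = 1.5 gives 0.5625/1.5625 = 0.360.

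**Chance of significance at n = 60.** The critical r is 0.254. By Fisher's z the chance is Φ(√57·atanh r − 1.96) plus the small opposite tail. At d = 1.0: √57 × atanh(0.200) = 7.550 × 0.2027 = 1.531, and Φ(1.531 − 1.960) = 0.334. A simulation (20,000 trials, 30 per arm) gives both the pooled and the arm-adjusted result.

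| d (both variables) | pooled r | pooled, Fisher z | pooled, simulated | arm-adjusted, simulated |
|---|---|---|---|---|
| 0.2 | 0.01 | 5% | 5% | 5% |
| 0.5 | 0.06 | 7% | 7% | 5% |
| 0.74 | 0.12 | 15% | not run | not run |
| 1.0 | 0.20 | 33% | 35% | 5% |
| 1.5 | 0.36 | 81% | 85% | 5% |

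With unequal effects of 1.5 and 0.8 SD, pooled r is 0.22 and 41% are significant. If only one variable responds (0 and 0.8), r is 0 and the rate is 5%. With 24 per arm (20% loss, assumed) the pooled rates are 28% at 1.0 SD and 76% at 1.5 SD. For scale, 30 per arm has 80% power for a between-arm difference of (1.960 + 0.842) × √(2/30) = 0.72 SD.

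**After arm adjustment, with varying response.** Suppose individual response varies and is shared by marker and outcome, as adherence would make it, with an assumed SD of 50% of the mean effect. With still no path from marker to outcome, the arm-adjusted correlation is significant in 8.5% of trials at 0.8 SD, 14% at 1.0 SD and 39% at 1.5 SD. Adjustment for arm is therefore necessary but does not establish a mechanism.

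**The case against.** The sentence is a single conditional in the Purpose section of an ethics form, and its verb is could. It is not an analysis rule, and the plan nowhere says that it would pool the arms. Cause-effect can fairly be read as the randomised effect of the product on outcomes and markers, which the design does support; on that reading only the mechanism claim goes too far. The induced correlation is also slight at modest effects. Stage 2 may never run, and section 14 requires an ethics amendment before any biological material is shipped, which would be a natural point to specify the analysis.

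Most of this stands, and it limits the point. A reader might infer that a spurious relationship appears whenever both variables respond to treatment. The documents do not support that: it holds for a pooled, unadjusted correlation, and the plan does not say which kind it would use.

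A reader might also multiply out the false positives. Five outcomes with 100 to 1,000 markers (an assumed count) at 0.05 would give 25 to 250 null pairs. That presumes no multiplicity control, whereas the metabolomic data analyses are deferred to an article not available here. The count cannot be put down as a defect of the plan.

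What the objection does not answer is the inference itself. Softening the verb or making the stage conditional does not turn correlated changes into evidence of mechanism, and no other section supplies the missing step.

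**Conclusion.** The point holds as a limit on what stage 2 can claim. Correlated changes in outcomes and markers do not show that a marker mediates an outcome. Causal effects of the product on each outcome and each marker, taken separately, remain supported by randomisation.

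The defect lies mainly in the inference, not in frequent false findings. A pooled correlation is close to the nominal 5% error rate at small effects and becomes commonly significant only when both effects are about 1 SD or more. These sizes rest on assumed effects, 1:1 allocation, two-sided tests, independent errors and complete data on 60 participants. Arm adjustment restores the nominal rate only if the treatment effect is uniform. Adherence, diet and recovery from the antibiotic prescribed before supplementation could each still move marker and outcome together.

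Severity is advisory.

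**What to change.** In section 8, restate the stage 2 marker-outcome relationships as exploratory and hypothesis-generating, and reserve causal wording for the randomised comparisons between arms.

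Before any stage 2 data exist, for example with the amendment that section 14 already requires before shipment, add a short analysis paragraph stating that:

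- each marker-outcome association is estimated in a model that includes arm and the baseline values of both variables;
- the false discovery rate is controlled across all pairs tested, unless the cited metabolomics methods already provide this, in which case say so;
- an association that remains after adjustment is not reported as a demonstrated mechanism.

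The cost is a more modest claim and one added paragraph, since no stage 2 association model exists yet to amend. No further visits, samples or participants are needed.

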60 participants ages 18-50 that have a BMI between 25.0-40.0 kg/m², who do not also have type 1 or type 2 diabetes mellitus (T1DM or T2DM) will be recruited. Exclusion criteria include: being vegetarian, vegan, carnivore, or keto; pregnancy or planning pregnancy during the study period; lactating women; having a history of inflammatory bowel disease, colon cancer; having been diagnosed with T1DM or T2DM; active cancer; currently participating in a weight loss intervention (dietetic or medication); use of antibiotics, antifungals, or antivirals in the last 3 months; currently taking metformin, GLP-1 agonists, insulin, or fiber supplement; having taken PPI, stimulant laxatives, probiotics, or immunosuppressants in the last month; history of recent (within 30 days) diarrhea illness (including bacterial or viral enteritis or enteric parasitic infection); having a known

hypersensitivity to any component of the study product; having an acute infection or inflammatory condition over the past 4 weeks; having >10% weight variation in the last 6 months; history of bariatric surgery in the past with exemption of laparoscopic band that has been removed.

12) Recruitment Procedure: Describe your recruitment strategies in great detail including how and where the potential participants will be approached and by whom. Will recruitment involve a point of contact on behalf of the study team? Who and how will recruitment material(s) be distributed? Describe precautions that will be taken to minimize the possibility of undue influence or coercion. Include copies of the recruitment emails, flyers, social media post, etc. in your submission as attachments or appendices following the recruitment guidelines.

TCU staff and students will be approached for recruitment via IRB-approved email (colleagues will be asked the favor to send the recruiting email to their current students), posters, flyers, and social media ads in English and Spanish. Posters and flyers will be posted in strategic locations such as dining halls, TCU cafeterias, dorms, bathrooms, gym, etc. as well as electronically on the Nutrition Department's webpage and Pendulum's webpage (supplement company). Ads will also be posted in strategic locations outside TCU such as gyms, cafeterias, health care centers, recreation centers, etc. Social media adds will be published in the professional Instagram page of the PI ([name]) and the professional Instagram and Facebook pages of the Nutrition Department (TCUNutrition and TCU Department of Nutritional Sciences, respectively), as well as through paid adds both in Facebook and Instagram. These recruitment methods will contain a QR code that links to a screening survey to evaluate participant eligibility. Precautions that will be taken to minimize undue influence or coercion: reiterate that participation is voluntary when dispersing recruitment materials, include all required elements aligned with TCU's recruitment guidelines for advertisement materials, and refrain from singling out students and staff that are familiar with or have personal ties to individuals on the research team.

13) Consenting Procedure: Describe the consenting procedure, whether participation is completely voluntary, whether the participants can withdraw at any time without penalty, the procedures for withdrawing, and whether an incentive (describe it) will be offered for participation. If students are used as participants, indicate an alternative in lieu of participation if course credit is provided for participation. If a vulnerable population is recruited, describe the measures that will be taken to obtain surrogate consent (e.g., cognitively impaired participants) or assent from minors and permission from parents of minors. If you need to request consent or HIPAA waivers you can do so in this section. If including Non-English-speaking participants, please include a plan to have consent documents translated after initial approval, by either student or faculty that is fluent in the desired language (give names and document translation and back translation) or a translation service/vendor. If the study involves deception explain the process of debriefing statement that will be given to participants and attach the script that will be used by the investigators to orally explain the study.

Advertisements, fliers, and emails contain a QR code that leads participants into a screening questionnaire which provides us with information regarding their eligibility to participate in this study. Email and phone number, but not other personal information, are collected in this screening form with the intention of contacting back the participants who are eligible. Eligible participants will be contacted through phone or email to schedule their first visit to the Kinesiology Department, Rickel Building 259. A trained, IRB-approved member of the research team will perform the informed consent. The consent document is attached to this protocol. Non-English-speaking participants may be included in this study. An IRB-Spanish version of the informed consent will be provided to the participants. The IRB Spanish version was written by [name] who is

fluent in Spanish and obtained her B.S. in México. [name] will conduct all Spanish-speaking informed consents. Students can take part in this project but will not receive extra credits. No vulnerable populations will be recruited.

The triple blinding nature of this study means that participants, researchers (including the PI), and statisticians cannot be made aware of the randomization allocation. Therefore, debriefing to participants can only take part until after data has been analyzed. Once all participants have finalized their interventions and all data has been analyzed, researchers will contact back participants to verbally give them the debriefing statement and inform them which supplement/placebo they received.

14) Study Procedures: Provide a chronological description of the procedures, tests, and interventions that will be implemented during the course of the study. Indicate the number of visits, length of each visit, and the time it would take to undergo the various tests, procedures, and interventions. If blood or tissue is to be collected, indicate exactly how much in volume and all procedures that will be done with collected samples. Describe when, where and how collection will take place. Flow diagrams may be used to clarify complex projects. For Non-TCU study team members please explain their study team role in detail. If the study involved deception justify the use of deception and explain why deception is necessary to achieve the goals of the study. Explain if alternative methods not involving use of deception were considered and why these methods are not being used.

STAGE 1

For stage 1, participants will come to TCU on three days total:

In the first visit, participants will come for 45 minutes to the Rickel Department where they will receive a complete explanation of the protocol and will process to sign the "Informed Consent to Participate in Research and Authorization to Collect, Use, and Share their Health Information" if agreeing to participate. Participants' height and weight will be measured to ensure they meet BMI inclusion criteria. Height will be measured using a standard stadiometer and weight will be measured using a standard calibrated digital scale. Their race will be asked to help in data interpretation. Height, weight, race and other information relevant to antibiotic prescription such as date of birth, allergies to medications, and preferred pharmacy will be collected at this time point using our document titled "checklist 2". All symbiotic and placebo bottles will be entirely similar with exemption of individual codes that will vary every 3 bottles. This is because each participant will be provided at the beginning of the study with 3 bottles (with similar code) to ensure enough supply for the 12-week supplement intervention. The company Pendulum will perform an *a priori* randomization of the entire study by using blocked randomization with randomly selected blocked sizes with the intention to reduce bias and ensure balance between groups. This randomization will be added into an Excel document in which they will specify the order of the participant in column 1 (example: Participant 001, Participant 002), the code of the bottles in column 2, and the interpretation of the code (placebo vs probiotic) in column 3. A researcher, independent from this study ([name]), will save in different protected locations (Box, secured laptop, protected USB) the randomization document. [name] will share with [name] an Excel document containing column 1 and column 2 of the provided document (the order of participant and the code of the bottles, without the interpretation of each code). [name] will use the supplement code as the participants' IDs and study data will be added to this Excel document. Both documents, from, [name] and from [name], will be merged at the end of the study, once data has been analyzed to figure out the intervention group to which each participant belonged. During the first

visit, depending on the order they enrolled, participants will receive the 3 bottles containing the assigned code. Participants will also be provided with two stool sample collection kits, a 3-day diet record form, a 3-day prescription of antibiotics (500 mg of generic Vancomycin every 8h), date for second appointment, and a start date for the antibiotic regimen. The 3-day antibiotic treatment provided prior to beginning the 12-week synbiotic intervention is given with the intention to increase the number of available bacterial niches (bacterial homes/space) and thus increase the engraftment of the newly ingested bacteria. Although participants will be asked to pay the cost of the generic antibiotic treatment initially (which should have an estimated cost of \$20-25), we will offset the cost of the antibiotic by providing the participants with a \$50 Amazon gift card in their second appointment, so they will not be responsible for any costs to participate in this study. This initial gift card is in addition to their \$100 Amazon gift card provided at the end of the study in appreciation for having taken part in this project. Their insurance will not be charged for any study-related testing; however, they are welcome to (but don't have to) use their insurance to buy the antibiotic. During this first visit, participants will have their 1) first 12h fasted blood collection and will be instructed to 2) fill out a 3 day food log before each stool sample collection, 3) collect a stool sample before the start of the antibiotic regimen, 4) collect a stool sample within 12-48 hours after the last dose of the antibiotic regimen, 5) bring both stool samples and diet records with them to the second appointment and, 6) fast 12 hours prior to the second appointment (refrain from the consumption of all food and liquids, except water). The first appointment is expected to take no greater than 45 minutes.

For the second visit, participants will meet researchers at the Rickel building. This appointment is expected to take approximately 45 minutes and includes the completion of a DEXA scan, an air displacement plethysmography test (via BOD POD), body weight measurement, the Beck Anxiety and Depression Inventories, the RED-9 questionnaire, and a blood draw. Participants will turn in their first (before antibiotic prescription initiation) and second (after antibiotic prescription completion) stool samples and food logs to researchers. The blood draw will consist on 2 serum separation tubes (10 mL each), 1 EDTA tube (3 mL), and 1 Zymo tube (3 mL). The time to complete each test is approximately as follows: 10 minutes for the blood draw, 10 minutes for the anxiety and depression survey, 20 minutes for the DEXA scan, and 5 minutes for an air displacement plethysmography test. Air displacement plethysmography tests via the BOD POD will be used to measure body fat percentage. Participants will be asked to wear minimal clothes and no shoes for the air displacement plethysmography test. The DEXA scans will be used to measure fat mass, visceral fat, lean mass, and bone mineral density. The DEXA scan uses a two-sided low emission X-ray to quantify lean body mass, fat mass, and bone density. To conduct the test, participants will be asked to void their bladder, remove all metal objects (piercings, rings, etc.) and shoes, and will lay supine on a padded table for approximately 6 minutes while the scanner moves down the length of the participant's body. Measurements will be conducted by a General Electric Certified DEXA Operator ([name] or [name]). Blood samples will be collected using sterile techniques and only by qualified investigators ([name] or [name]). Blood samples will be used to measure fasting glucose, fasting insulin, and HbA1C. Blood will be sampled using venipuncture. The venipuncture samples will be collected using a traditional blood draw needle to extract blood from a vein in the antecubital region of the arm. Two 10 mL vials of blood will be collected, centrifuged to separate the serum. One of those tubes will be stored in a -80°C freezer in the Exercise Physiology Laboratory (Rickel 259) whereas the other will be transported to BioReference for fasting glucose and insulin analysis. The 3 mL for EDTA analysis will also be transported to BioReference for HbA1C analysis. The Zymo collection tube (3 mL) will be stored at the Rickel 259 building. All blood collection vials and plasma/serum containers will be

labeled using participant numbers (deidentified) for participant privacy. The leftover blood samples will be stored in the laboratory for 10 years from date of collection at which point they will be discarded as biohazard waste. Participants agree to allow their deidentified samples to be used for future research by signing the informed consent. These procedures have been approved by the TCU Institutional Biosafety Committee (IBC Protocol). At the end of the second appointment, participants will be provided with the 12 weeks of the probiotic+prebiotic supplement. Each person will receive 3 bottles (one per month) with the three of them having the same ID, this same ID will be used to identify all questionnaires and samples obtained from that person. This ID will also be different between each participant. Participants will also be instructed to 1) record everything they eat for 72 hours before stool sample collection, 2) collect a stool sample within 24 hours of finishing the last dose of the intervention, 3) bring the stool sample, diet record, and remnant of their supplement or placebo with them to the third appointment, and 4) fast 12 hours prior to the third appointment (refrain from the consumption of all food and liquids, except water).

The third and final appointment is expected to also take approximately 45 minutes and will include a replication of all tests conducted in the second appointment (completion of a DEXA scan, an air displacement plethysmography test [via BOD POD], body weight measurement, the Beck Anxiety and Depression Inventories, the RED-9 questionnaire, and a blood draw [consisting on 2 serum separation tubes of 10 mL each, 1 EDTA tube of 3.5 mL, and 1 Zymo tube of 3mL]). Participants will turn in their third and final stool sample, as well as the remnant of their supplements or placebo for analysis of adherence and compliance. Participants will receive a \$100 Amazon gift card at the end of the study in compensation for their time. After all stool samples have been collected, they will be sent in the same batch to the Alkek Center for Metagenomics and Microbiome Research (CMMR) at Baylor College of Medicine in Houston for posterior whole genome sequencing analysis.

Whole Genome Shotgun Metagenomic Sequencing will reveal not only the characterization of all the species present in the sample down to the strain level but also their functionality according to their genetic capacity. Unlike 16S rRNA which sequences only a specific region of the ribosome, whole metagenome sequencing sequences all the genomic material present in the sample and thus allows for higher resolution down to the strain level. Whole metagenome sequencing also allows for the identification of viruses and other important microorganisms whose importance we are just now starting to understand. That being said, the main goal of incorporating whole metagenome sequencing in this study is to explore the effect of the probiotic on the gut microbiota composition and functionality when it is preceded by short antibiotic exposure. The following represents the whole metagenome sequencing methods employed by the CMMR at Baylor College of Medicine.

CMMR Bioinformatics WGS Pipeline. Raw data files in binary base call (BCL) format are converted into FASTQs and demultiplexed based on the dual-index barcodes using the Illumina 'bcl2fastq' software. Demultiplexed raw fastq sequences are processed using BBduk (sourceforge.net/projects/bbmap/; BBMap version 38.82) to quality trim, remove Illumina adapters and filter PhiX reads. Trimming parameters are set to a k-mer length of 19 and a minimum Phred quality score of 25. Reads with a minimum average Phred quality score below 23 and length shorter than 50 bp after trimming are discarded. The trimmed fastqs are mapped to a combined PhiX (standard Illumina spike in) and host reference genome database using a two-step BBTools approach (sourceforge.net/projects/bbmap/; BBMap version 38.82). Briefly, the trimmed reads are first processed through the bloomfilter script, with a strict k=31 to remove reads identified as human. The remaining reads are mapped to the reference genome

with BBMap using a k-mer length of 15, the bloom filter enabled, and fast search settings in order to determine and remove host/PhiX reads.

Taxonomic profiling – MetaPhlAn2. Taxonomic profiling of the sequenced samples is done using MetaPhlAn2 (4). Processed fastq reads are first mapped against the MetaPhlAn2 marker gene database (mpa_v20_m200) using bbmap (3) with the bloom filter enabled and fast search settings. Each sample is run through the metaphlan.py script to generate the kingdom-specific taxonomic profile per sample, using the flag to generate relative abundances and estimated read counts. The MetaPhlAn2 utility scripts are employed to merge the output for all samples into a single sample per taxon table for each kingdom and relative abundance and estimated read count output. Finally, the tables are converted into biom-format for further statistical analysis.

Taxonomic profiling – MetaPhlAn3. Taxonomic profiling of the sequenced samples is done using MetaPhlAn3 (7). Processed fastq reads are first mapped against the MetaPhlAn3 marker gene database (mpa_v30_CHOCOPhIAn_201901) using bbmap (3) with the bloom filter enabled and fast search settings. Each sample is run through the metaphlan.py script to generate the kingdom-specific taxonomic profile per sample, using the flag to generate relative abundances and estimated read counts. The MetaPhlAn3 utility scripts are employed to merge the output for all samples into a single sample per taxon table for each kingdom and relative abundance and estimated read count output. Finally, the tables are converted into biom-format for further statistical analysis.

